7.9.3 Vital Signs and Physical Examinations

Vital signs (systolic and diastolic blood pressure, temperature, heart rate, and respiratory rate), weight, and body mass index will be summarized descriptively at baseline and all post baseline study visits by treatment group. Change from baseline to all post baseline study visits will be summarized descriptively by treatment group.

Physical examinations (general appearance; skin; head, ears, eyes, nose, and throat; neck; lymph nodes; chest (including lungs); heart; abdomen; extremities; nervous system; and musculoskeletal system) at baseline will be summarized. Shifts from baseline to post baseline study visits in each body system/site will be summarized by treatment group.

7.9.4 Suicidality

Suicidality assessed by ABC-I will be summarized descriptively at baseline and all post baseline study visits by treatment group. Change from baseline to all post baseline study visits also will be summarized descriptively by treatment group.

[figure not shown]
7.9.5 Seizure Diary Data

Seizure diary data will be summarized descriptively at baseline and all post baseline study visits by treatment group. Additionally, the seizure frequency (expressed as a 28-day frequency) will be calculated for the following study periods: Baseline (Screening to Day 1), Week 6 (Day 1 to Week 6 visit date), and Week 12 (Week 6 visit date + 1 to Week 12 visit date). Percent change in seizure frequency from baseline to all post baseline study visits also will be summarized descriptively by treatment group.

7.10 Other Analyses

7.10.1 Concomitant Medications

Concomitant medications will be coded using the World Health Organization Drug Dictionary (WHO-DD) and will be summarized according to their WHO-DD Anatomic Therapeutic Chemical class level 4 and preferred drug name within Anatomic Therapeutic Chemical class level 4. The number and percentage of subjects who took at least 1 medication post baseline as well as the number and percentage of subjects who took each type of medication will be presented for each treatment group.

7.11 Interim Analyses

No interim analyses of efficacy data are planned for this study.

7.12 Statistical Testing and Significance Level

The primary analysis will be performed on the FAS and the PPS. However, the PPS analysis will only be considered a sensitivity analysis.

Inferential treatment comparison of the primary efficacy endpoint, CGI-I-AS at Week 12, will be conducted at the 0.050 level of significance using a 2-tailed test. If the null hypothesis of no

treatment difference for the primary endpoint is rejected, the alpha (0.05) will be passed to the significance testing for the key efficacy endpoints, CGI-I-AS response (at least minimally improved) at Week 12 and CGI-I-AS response (at least much improved) at Week 12, which will be tested using the corresponding 2-sided tests at 0.05 level of significance in a fixed sequence. If and only if the null hypothesis of no treatment difference based on CGI-I-AS response (at least minimally improved) is rejected at 0.05 level of significance, testing will continue and the null hypothesis of no treatment difference based on CGI-I-AS response (at least much improved) will be tested at 0.05 level of significance.

No formal statistical testing of other secondary endpoints will be performed. All *P* values presented for secondary and tertiary endpoints will be considered descriptive in nature.

7.13 Missing Data Handling and Sensitivity Analysis

The MMRM model used in the analysis of key efficacy endpoints implicitly adjusts for missing data. If missing data are 5% or more for the primary endpoint, a sensitivity analysis will be performed, with missing outcomes be imputed in the analysis models. Multiple imputation techniques will be used for imputation, under the assumption of data missing not at random. Additionally, a tipping point analysis will be performed. Details will be specified in the SAP.

Rules for imputation of missing dates for AEs and concomitant medications will be stated in the SAP.

8 Data Quality Assurance

This study will be conducted according to the International Council for Harmonisation (ICH) E6 (R2) risk and quality processes described in the applicable procedural documents. The quality management approach to be implemented in this study will be documented and will comply with the current ICH guidance on quality and risk management.

Standard operating procedures are available for all activities relevant to the quality of this study. Designated staff will be responsible for implementing and maintaining quality assurance and quality control systems to ensure that the study is conducted and that data are generated, documented, and reported in compliance with the study protocol, Good Clinical Practice (GCP), and Good Laboratory Practice requirements as well as applicable regulatory requirements and local laws, rules, and regulations relating to the conduct of the clinical study.

An authorized quality assurance auditor will audit the study data and procedures at periodic intervals as indicated. Domestic or foreign regulatory authorities, the IRB or IEC, and a Sponsor-authorized auditor may request access to all study documentation for an on-site inspection or audit. The investigator must notify the Sponsor of any regulatory authority inspections and forward copies of the inspection report to the Sponsor.

Electronic data systems will be in accordance with applicable aspects of US Title 21 Code of Federal Regulations (CFR) Part 11, ICH Guidelines, GCP, local laws and legislation, and the Health Insurance Portability and Accountability Act.

8.1 On-Site Audits

At any time, quality assurance representatives of the Sponsor and/or regulatory bodies may visit the unit to carry out an audit of the study in compliance with regulatory guidelines and company policy. Such audits will require access to study records, documentation, and regulatory files. At all times, subject privacy will be of utmost importance and maintained. Typically, sufficient (minimum of 2 weeks) notice will be given to the investigator to prepare for the visit.

8.2 Data Management

As part of the responsibilities assumed by participating in the study, the investigator agrees to maintain adequate case histories for the subjects treated as part of the research under this protocol. The investigator agrees to maintain accurate eCRFs and source documentation as part of the case histories. These source documents may include such documents as questionnaire results, [REDACTED] and computerized or otherwise automated assessments [REDACTED]

Investigative site staff will enter subject data into Medidata RAVE® (the eCRF program). The analysis data sets will be a combination of these data and data from other sources (e.g., laboratory data).

Clinical data management will be performed in accordance with applicable Sponsor standards and data cleaning procedures to ensure the integrity of the data, e.g., removing errors and inconsistencies in the data. Adverse event terms will be coded using MedDRA, an internal validated medical dictionary, and concomitant medications will be coded using the World Health Organization Drug Dictionary. Concomitant medications will be coded using the World Health Organization Drug Dictionary.

After database lock, each study site will receive a CD-ROM containing all its site specific eCRF data as entered into the EDC system for the study, including full discrepancy and audit history. Additionally, a CD-ROM copy of all the site's data from the study will be created and sent to the Sponsor for storage. [REDACTED] will maintain a duplicate CD-ROM copy for their records. In all cases, subject initials will not be collected or transmitted to the Sponsor.

9 Ethics

9.1 Independent Ethics Committee or Institutional Review Board

Federal regulations and the ICH guidelines require that approval be obtained from an IRB/IEC before participation of human subjects in research studies. Before study onset, the protocol, informed consent, assent, advertisements to be used for the recruitment of study subjects, and any other written information regarding this study to be provided to the subject or the subject's legal guardian must be approved by the IRB/IEC. Documentation of all IRB/IEC approvals and of the IRB/IEC compliance with ICH harmonised tripartite guideline E6 (R2): GCP will be maintained by the site and will be available for review by the Sponsor or its designee.

All IRB/IEC approvals should be signed by the IRB/IEC chairman or designee and must identify the IRB/IEC name and address, the clinical protocol by title or protocol number or both, and the date approval or a favorable opinion was granted.

The investigator is responsible for providing written summaries of the progress and status of the study at intervals not exceeding 1 year or otherwise specified by the IRB/IEC. The investigator must promptly supply the Sponsor or its designee, the IRB/IEC, and, where applicable, the institution, with written reports on any changes significantly affecting the conduct of the study or increasing the risk to subjects.

9.2 Ethical Conduct of the Study

The study will be performed in accordance with the ethical principles that have their origin in the Declaration of Helsinki, ICH GCP, the protocol, and all applicable regulations.

9.3 Subject Information and Consent

A written informed consent in compliance with applicable regulatory authority regulations shall be obtained from the LAR/caregiver of a minor before the subject enters the study or any unusual or nonroutine procedure that involves risk to the subject is performed. For minors an assent document will be presented, and assent will be obtained before the subject participates in any study procedure. Informed consent and assent template documents may be provided by the Sponsor to investigative sites. If any institution-specific modifications to study-related procedures are proposed or made by the site, the consent and assent should be reviewed by the Sponsor or its designee or both before IRB submission. Once reviewed, the consent and assent will be submitted by the investigator to his or her IRB for review and approval before the start of the study. If the ICF is revised during the study, all active participating subjects and LAR/caregivers (as applicable) must sign the revised forms.

Before recruitment and enrollment, each prospective subject's LAR/caregiver and subject (as applicable) will be given a full explanation of the study and will be allowed to read the approved ICF/assent. Once the investigator is assured that the LAR/caregiver and subject understand the implications of participating in the study, the LAR/caregiver and subject will be asked to give consent/assent to participate in the study by signing/approving the ICF/assent.

The investigator shall retain the signed original ICFs/assents and give copies of the signed original forms to the LAR/caregivers and subjects, as applicable.

10 Investigator's Obligations

The following administrative items are meant to guide the investigator in the conduct of the study but may be subject to change based on industry and government standard operating procedures, working practice documents, or guidelines. Changes will be reported to the IRB/IEC but will not result in protocol amendments.

10.1 Confidentiality

All laboratory specimens, evaluation forms, reports, and other records will be identified in a manner designed to maintain subject confidentiality. All records will be kept in a secure storage area with limited access. Clinical information will not be released without the written permission of the subject (or the subject's legal guardian or LAR/caregiver), except as necessary for monitoring and auditing by the Sponsor, its designee, the US Food and Drug Administration (FDA) or other applicable regulatory agency, or the IRB/IEC.

The investigator and all employees and coworkers involved with this study may not disclose or use for any purpose other than performance of the study any data, record, or other unpublished, confidential information disclosed to those individuals for the purpose of the study. Prior written agreement from the Sponsor or its designee must be obtained for the disclosure of any said confidential information to other parties.

10.2 Financial Disclosure and Obligations

Investigators are required to provide financial disclosure information to allow the Sponsor to submit the complete and accurate certification or disclosure statements required under 21 CFR 54. In addition, the investigator must provide to the Sponsor a commitment to promptly update this information if any relevant changes occur during the study and for 1 year following the completion of the study.

Neither the Sponsor nor [REDACTED] is financially responsible for further testing or treatment of any medical condition that may be detected during the screening process. In addition, in the absence of specific arrangements, neither the Sponsor nor [REDACTED] is financially responsible for further treatment of the subject's disease.

10.3 Investigator Documentation

Prior to beginning the study, the investigator will be asked to comply with ICH E6 (R2) 8.2 and Title 21 of the CFR by providing essential documents, including but not limited to the following:

- IRB/IEC approval.
- Original investigator-signed investigator agreement page of the protocol.
- Form FDA 1572, fully executed, and all updates on a new fully executed Form FDA 1572.
- Curriculum vitae for the investigator and each sub investigator listed on Form FDA 1572.
- Financial disclosure information to allow the Sponsor to submit complete and accurate certification or disclosure statements required under 21 CFR 54. In addition, the investigators must provide to the Sponsor a commitment to promptly update this information if any relevant changes occur during the course of the investigation and for 1 year after the completion of the study.
- IRB/IEC-approved informed consent and assent, samples of site advertisements for recruitment for this study, and any other written information regarding this study that is to be provided to the subject or legal guardian.
- Laboratory certifications and normal ranges for any local laboratories used by the site, in accordance with 42 CFR 493.

10.4 Study Conduct

The investigator agrees that the study will be conducted according to the principles of ICH E6 (R2). The investigator will conduct all aspects of this study in accordance with all national, state, and local laws or regulations. Study information from this protocol will be posted on publicly available clinical trial registers before the enrollment of subjects begins.

10.5 Adherence to Protocol

The investigator agrees to conduct the study as outlined in this protocol in accordance with ICH E6 (R2) and all applicable guidelines and regulations.

10.6 Adverse Events and Study Report Requirements

By participating in this study, the investigator agrees to submit reports of SAEs to the Sponsor and/or IRB/IEC according to the timeline and method outlined in the protocol. In addition, the investigator agrees to submit annual reports to the study site IRB/IEC as appropriate.

10.7 Investigator's Final Report

Upon completion of the study, the investigator, where applicable, should inform the institution; the investigator/institution should provide the IRB/IEC with a summary of the study's outcome and the Sponsor and regulatory authority(ies) with any reports required.

10.8 Records Retention

Essential documents should be retained until at least 2 years after the last approval of a marketing application in an ICH region and until there are no pending or contemplated marketing applications in an ICH region or at least 2 years have elapsed since the formal discontinuation of clinical development of the investigational product. These documents should be retained for a longer period, however, if required by the applicable regulatory requirements or by an agreement with the Sponsor. It is the responsibility of the Sponsor to inform the investigator/institution as to when these documents no longer need to be retained.

10.9 Publications

After completion of the study, the data may be considered for reporting at a scientific meeting or for publication in a scientific journal. In these cases, the Sponsor will be responsible for these activities and will work with the investigators to determine how the manuscript is written and edited, the number and order of authors, the publication to which it will be submitted, and other related issues. The Sponsor has final approval authority over all such issues.

The data are the property of the Sponsor and cannot be published without prior authorization from the Sponsor, but data and publication thereof will not be unduly withheld.

11 Study Management

11.1 Monitoring

11.1.1 Independent Data Monitoring Committee

An IDMC will monitor the study (Section 6.5): it will include 3 independent representatives including a chairperson, a pediatric epileptologist, and a biostatistician. The IDMC charter includes the details for the IDMC including responsibilities, qualifications, and key processes. The IDMC responsibilities will include (but are not limited to) the following:

- Staged Enrollment Review Meetings. Subject assignment to treatment will be stratified and staged by age and gated by the IDMC via the evaluation of sentry subjects (Section 5.1). No age cohort may begin treatment without IDMC review of tolerability in sentry subjects in the previous older cohort.
- Meet periodically to review aggregate and individual subject data related to safety, data integrity, and overall conduct of the trial.
- Work with the Independent Statistical Center to determine the data presentations (tables, listings, and figures) that are necessary for the IDMC to monitor study conduct and safety.
- Review and evaluate the content of all data presentations received before each IDMC Meeting.
- Contribute to closed session reviews and recommendations.

11.1.2 Clinical Trial Steering Committee

The CTSC will include approximately 5 independent representatives, including a chairperson, representatives with relevant expertise in pediatric psychiatry, pediatric epileptology, pediatric neurology and psychology, and a parent of a child with AS. In addition, 2 Sponsor representatives will be included on the CTSC. The CTSC responsibilities will include (but are not limited to) the following:

- Conduct interim review of the trial's progress including updated data on recruitment and data quality.
- Review recommendations of the IDMC including but not limited to:

- Safety issues which may suggest risk to currently enrolled or future subjects
 - Recommendations to modify or terminate the trial if, following review of the data, there are safety or efficacy concerns.
- Monitor compliance with IDMC recommendations.
 - Monitor recruitment data and accrual within relevant subsets, screen failures, dropouts, and losses to follow-up overall and by study site.
 - Monitor compliance with the protocol and protocol violations by subjects and investigators.
 - Advise on protocol modifications suggested by investigators or Sponsors (e.g., amendments to inclusion criteria, trial endpoints, or sample size).
 - Monitor planned sample size assumptions.
 - Monitor continuing appropriateness of subject information.
 - Assess the impact and relevance of external evidence.

11.1.3 Monitoring of the Study

The clinical monitor, as a representative of the Sponsor, has the obligation to follow the study closely. In doing so, the monitor will visit the investigator and study site at periodic intervals, in addition to maintaining necessary telephone and letter contact. The monitor will maintain current personal knowledge of the study through observation, review of study records and source documentation, and discussion of the conduct of the study with the investigator and personnel.

All aspects of the study will be carefully monitored, by the Sponsor or its designee, for compliance with applicable government regulation with respect to current GCP and current standard operating procedures.

11.1.4 Inspection of Records

Investigators and institutions involved in the study will permit study-related monitoring, audits, IRB/IEC review, and regulatory inspections by providing direct access to all study records. In the event of an audit, the investigator agrees to allow the Sponsor, representatives of the Sponsor, or a regulatory agency access to all study records.

The investigator should promptly notify the Sponsor and [REDACTED] of any audits scheduled by any regulatory authorities and promptly forward copies of any audit reports received to the Sponsor.

11.2 Management of Protocol Amendments and Deviations

11.2.1 Modification of the Protocol

Any changes in this research activity, except those necessary to remove an apparent, immediate hazard to the subject, must be reviewed and approved by the Sponsor or its designee.

Amendments to the protocol must be submitted in writing to the investigator's IRB/IEC for approval before subjects can be enrolled into an amended protocol.

11.2.2 Protocol Deviations

The investigator or designee must document and explain in the subject's source documentation any deviation from the approved protocol. The investigator may implement a deviation from, or a change of, the protocol to eliminate an immediate hazard to study subjects without prior IRB/IEC approval. As soon as possible after such an occurrence, the implemented deviation or change, the reasons for it, and any proposed protocol amendments should be submitted to the IRB/IEC for review and approval, to the Sponsor for agreement, and to the regulatory authorities, if required.

A deviation from the protocol is an unintended or unanticipated departure from the procedures or processes approved by the Sponsor and the IRB/IEC and agreed to by the investigator. A significant deviation occurs when there is nonadherence to the protocol by the subject or investigator that results in a significant, additional risk to the subject. Significant deviations can include nonadherence to inclusion or exclusion criteria, or nonadherence to FDA regulations or ICH GCP guidelines, and will lead to the subject being withdrawn from the study (Section 4.2).

Protocol deviations will be documented by the clinical monitor throughout the course of monitoring visits. Principal investigators will be notified in writing by the monitor of deviations. The IRB/IEC should be notified of all protocol deviations in a timely manner.

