4.2 Discontinuation and Withdrawal of Subjects

Subjects who discontinue treatment during the study will be encouraged by investigators to continue to participate in all scheduled study site visits and assessments, and study data will be collected for these subjects per protocol. Study drug administration may be stopped early at the discretion of the investigator (or designee) if a subject does not tolerate the dosing regimen. Every effort should be made to keep subjects in the study.

Early withdrawal of a subject from the study (before Week 12) will initiate procedures for ending all subject participation in the study, including EOT and EOS assessments (Section 4.2.2). For subjects who are withdrawn early, an EOT visit should be conducted within 2 weeks after the last day of study drug. After completing the EOT visit, an EOS phone visit should be completed within 2 weeks after completing the EOT visit. The duration of the study is defined for each subject as the date signed written informed consent is provided through the EOS phone visit. The Sponsor may continue to enroll subjects to account for discontinuations, withdrawals, early terminations, etc.

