3.2 Analysis Populations and Subgroups

3.2.1 Definition of Analysis Populations

The following analysis sets, with the exception of the Intent-to-treat and Safety Set, will only include subjects 4 to 12 years old (inclusive) at screening. The baseline and safety analyses for subjects 2 to 3 years old (inclusive) at screening will be conducted separately.

Intent-to-Treat Analysis Set

The intent-to-treat set (ITT) will consist of all subjects who are randomized (subjects aged 4 to 12 years old (inclusive) or enrolled (subjects aged 2 to 3 years old (inclusive) and meet all inclusion and exclusion criteria), whether or not study drug is received. Subjects aged 4 to 12 years old (inclusive) will be analyzed according to their randomized treatment.

Full Analysis Set

The full analysis set (FAS) will include all subjects aged 4 to 12 years old (inclusive) who are randomized, receive at least 1 dose of study drug, and have at least 1 post-baseline assessment of the primary efficacy endpoint. The FAS will be used for efficacy analyses based on the randomized treatment for each subject.

Per Protocol Set

The per protocol set (PPS) is a subset of the FAS that includes subjects who complete the Week 12 CGI-I-AS assessment (with appropriate visit mapping as shown in Table 2) and have no major protocol deviations that are deemed to impact efficacy. These violations include but are not limited to violations of inclusion/exclusion criteria deemed to impact efficacy, inadequate study drug compliance over the dosing period as determined from the dosing information in the eCRF, usage of prohibited concomitant medications, and incorrect randomization. Additionally, other relevant protocol deviations, such as early termination or interruption of treatment, may be identified for review.

Prior to database lock and unblinding, there will be a meeting to review all protocol deviations to determine PPS exclusions. The threshold for percent compliance that would be considered inadequate and would result in exclusion from the PPS will also be determined in this meeting following review of the relevant compliance

information. The PPS will be used for efficacy analyses based on the randomized treatment for each subject.

Safety Set

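### Protocol 11.2.2 makes study withdrawal mandatory after a significant deviation, which Sections 4.2 and 4.2.1 do not, and so can end collection of the Week 12 primary rating

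*Protocol*

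**What the plan says.** Protocol 11.2.2 (Protocol Deviations) defines a significant deviation as "nonadherence to the protocol by the subject or investigator that results in a significant, additional risk to the subject". It gives eligibility breaches as one example, then states a second example and the consequence together, without qualification: "nonadherence to FDA regulations or ICH GCP guidelines, and will lead to the subject being withdrawn from the study (Section 4.2").

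Protocol 4.2, the section cited, takes a different line. On subjects in general: "Every effort should be made to keep subjects in the study". On those who stop study drug: "Subjects who discontinue treatment during the study will be encouraged by investigators to continue to participate in all scheduled study site visits and assessments", with their data still collected. It then describes study withdrawal as a separate event: "Early withdrawal of a subject from the study (before Week 12) will initiate procedures for ending all subject participation in the study". For a child withdrawn early, "an EOT visit should be conducted within 2 weeks after the last day of study drug", followed by an end-of-study call. Section 4.2.1 lists reasons for which a subject *may* be withdrawn, including ceasing to meet the eligibility criteria.

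SAP 3.2.1 defines the full analysis set (FAS) by randomisation, at least one dose and at least one post-baseline CGI-I-AS, with no exclusion for deviations. Deviations judged to affect efficacy remove a child from the per protocol set (PPS) only, at a meeting before unblinding. Of these it says: "These violations include but are not limited to violations of inclusion/exclusion criteria deemed to impact efficacy".

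**The concern.** The same child can fall under opposite instructions. A site that reads 11.2.2 ends participation; a site that reads 4.2 tries to keep the child attending. 11.2.2 also merges two decisions that 4.2 keeps apart: whether study drug continues, and whether outcome data are still collected.

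What is at stake is the primary outcome. Ending follow-up by rule can turn a deviation into a missing Week 12 CGI-I-AS that could have been collected at an already scheduled visit. The deviation may be the investigator's, in which case data are lost for a reason unrelated to the child. It may also arise after randomisation: exclusion criterion 4 bars certain sleep drugs during the study, and inclusion criterion 8 requires stable regimens throughout. A breach of that kind could be related to response or tolerability. If it were judged significant, the resulting gap would sit less easily with the missing-at-random assumption behind the primary model.

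**Working it through.** The plan states no figure on this point, so there is none to reproduce. The check sets the passages side by side, follows a withdrawn child through the analysis rules, and then gives a sense of scale.

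**1. The withdrawal rules compared**

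| Place | Applies to | Force | Effect |
|---|---|---|---|
| Protocol 11.2.2 | Significant deviations, by subject or investigator | *will* | Withdrawal from the study, citing 4.2 |
| Protocol 4.2 | All subjects | *should* | Keep in the study |
| Protocol 4.2 | Those who stop study drug | encouraged | All visits continue, data collected |
| Protocol 4.2.1 | Listed reasons, including eligibility no longer met | *may* | Withdrawal from the study |
| SAP 3.2.1 | Major deviations affecting efficacy | decided before unblinding | Out of the PPS; no FAS exclusion |

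Only 11.2.2 makes withdrawal mandatory, and the section it cites does not.

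**2. What happens to the Week 12 value**

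Inputs: the end-of-treatment (EOT) visit is due within 14 days of the last dose (Protocol 4.2). The primary mapping assigns Days 22 to 64 to Week 6 and Days 65 to 92 to Week 12 (SAP 3.1.8, Table 2). Missing CGI-I-AS is not imputed in the primary analysis, which relies on the mixed model under missing at random (SAP 3.8.6). The check assumes that the EOT visit takes place on time and includes the CGI-I-AS.

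Latest EOT day = last dose day + 14.

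- Last dose on Day 50: 50 + 14 = 64. This is at best a Week 6 record, so Week 12 is missing.
- Last dose on Day 51: 51 + 14 = 65. This is the first day on which an on-time EOT can count as Week 12.
- Last dose on Days 51 to 64: it depends on when in the two weeks the visit is held.
- Last dose on Days 65 to 78: every on-time EOT falls within Days 65 to 92 (78 + 14 = 92), so Week 12 is present.

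A child withdrawn with no post-baseline CGI-I-AS at all leaves the FAS as well. The supportive mapping (SAP Table 3) treats any rating after Day 43 as Week 12 and so recovers some of these children, but not in the primary analysis.

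**3. Scale**

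Inputs: about 90 children randomised (Protocol synopsis, SAP 2.2.1). Multiple imputation is added when more than 3% of Week 12 values are missing. A tipping-point analysis comes into play above 5%, which SAP 3.8.6 also makes conditional on a significant imputed result. The denominator is taken as 90 for illustration.

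- One child: 1/90 = 1.1%.
- 3% of 90 = 2.7, so the smallest count above the first trigger is 3 (3/90 = 3.3%).
- 5% of 90 = 4.5, so the smallest count above the second is 5 (5/90 = 5.6%).

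These counts are missing values from all causes. They locate the triggers and do not predict how many children 11.2.2 would remove. The documents give no such number, and the sample-size section (Protocol 7.3) is not in the public text, so neither bias nor loss of power can be calculated.

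**The case against.** The strongest reply is that 11.2.2 is a narrow safety rule. It applies only where nonadherence creates significant additional risk; lesser departures are simply recorded, as with a gabapentin dose change in Protocol 5.8.1. The reference to 4.2 can be read as pointing to the EOT and end-of-study procedures, which 4.2 does contain. The continued-visits sentence in 4.2 covers children who stop drug, and only encourages them. A withdrawn child with a Week 6 rating stays in the FAS, and the mixed model uses that rating. Crossing 3% or 5% missing only adds analyses that are already planned.

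All of that limits the size of the problem. It leaves *will* against *may*, the general instruction to keep children in the study, and no statement of whether ratings continue after a significant deviation.

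Several stronger readings are tempting but are not supported:

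- A reader might infer that any eligibility or GCP breach forces withdrawal. 11.2.2 says significant deviations *can include* these; the risk threshold still applies.
- A reader might expect pandemic conduct to swell the numbers. The pandemic addendum has late baseline visits recorded as deviations without automatic screen failure, and SAP Section 1 expects remote visits and local laboratories and analyses what is observed. Nothing shows that these carry significant additional risk.
- A reader might conclude that the FAS-versus-PPS comparison is emptied. Most listed PPS exclusions, such as poor compliance or incorrect randomisation, need not trigger 11.2.2. The two classes overlap mainly at eligibility.
- A reader might set such withdrawals against the gap of 10 between 90 randomised and 80 evaluable. Evaluable there means completing 12 weeks of treatment, so a child off drug but still followed would not count either. Protocol 4.2 also lets the sponsor keep enrolling to cover losses.

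**Conclusion.** The inconsistency is real and worth correcting. Protocol 11.2.2 imposes a withdrawal that its cited section does not contain and that 4.2.1 leaves optional, while the SAP has no deviation exclusion from the primary analysis set. Applied as written, it can leave the primary Week 12 value missing for a randomised child. If the EOT visit is on time, that is certain for a last dose on Day 50 or earlier and possible for one on Days 51 to 64.

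The size is unknown and may be small, because the rule is limited to deviations that add significant risk and their number is not given. The 1.1% per child is a scale, not an estimate. The case for changing the text is that the loss is avoidable and cheap to prevent; no material bias or loss of power has been shown.

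**What to change.** Reconcile Protocol 11.2.2 with 4.2 and 4.2.1, settling *will* against *may*. In the same sentence, separate two things: what happens to study drug after a significant deviation, and what happens to data collection. For the second, state that where the child remains willing and able to attend, the scheduled Week 6 and Week 12 CGI-I-AS ratings are still collected. The deviation itself then goes to the pre-unblinding PPS review already set out in SAP 3.2.1. The grounds for stopping drug or withdrawing a child remain the sponsor's decision, and this point proposes no change to them.

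The cost is about one protocol sentence in an amendment and a note to sites. No visits are added beyond those already scheduled, and the SAP's analysis sets need no change.
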